5.4 Covariate adjustment

No covariate adjustment will be used in the statistical analysis. Non-parametric unadjusted analyses will be performed instead.

Because randomization was stratified by maximum CRP, covariate adjustment would usually be recommended, especially for the analysis of the co-primary outcomes **P1** and **P2**, as this usually leads to power gains [10, 16]. However, we expect very few hospital readmissions due to bacterial infection (**P1**) in each group, whatever the maximum CRP. This specific context has two important consequences for the analysis of outcome **P1**. First, potential loss of power is expected to be negligible. Second, the typical large sample approximations required to ensure correct coverage probability and type-I error control using a “covariate-adjusted” approach would be very questionable.

Covariate adjustment could also be recommended to make the “no unmeasured confounding” assumption more plausible, for the analysis of the PP estimand using the “Per protocol analysis set” (defined in Section 6). Here again, the rationale for no covariate adjustment is that we expect very few hospital readmissions due to bacterial infection (**P1**), making “covariate-adjusted” inference likely unreliable. Instead, a sensitivity analysis will be provided (see Section 7.1.1). Additionally, descriptive statistics will be provided of newborns included in, and excluded from, the “Per protocol analysis set”. This will facilitate the assessment of the risk of selection bias, which could potentially lead to confounding (see Section 10.2.5).

A very large power is expected for the analysis of the co-primary outcome **P2**, hence there is no real power gain incentive to use covariate adjustment in the analysis of **P2**. Additionally, we are not aware of well-known, model-robust and recommended methods using covariate adjustment to compare medians. Finally, the analysis of **P2** aims to establish superiority and unadjusted ITT analyses are generally conservative when the aim is to show superiority.

6 Analysis Sets

- The “**All participants analysis set**” (**All**) consists of all randomized participants.
- The “**Per protocol analysis set**” (**PP**) consists of all randomized participants that have actually received the intervention (“individualized” or “standard”) as they should according to the protocol. Deviations from the protocol that are used to exclude patients from this analysis sets are listed in Section 10.2.5.
- The “**Breastfeeding-2d analysis set**” (**B2**) consists of all randomized participants that do not have missing data about breastfeeding at 2 days after end of initial antibiotic treatment (i.e., no missing data for **E6**).⁶
- The “**Breastfeeding-21d analysis set**” (**B21**) consists of all randomized participants that do not have missing data about breastfeeding at 21 days after end of initial antibiotic treatment (i.e., no missing data for **E7**).⁶
- The “**CRP-2-ITT analysis set**” (**CRP2**) consists of all randomized participants that do not have missing data about CRP at 2 days after treatment stopped (i.e., no missing data for **E8**).⁶
- The “**Breastfeeding-2d-PP analysis set**” (**B2-PP**) consists of all randomized participants that are in both the “Per protocol analysis set” and the “Breastfeeding-2d-ITT analysis set”.
- The “**Breastfeeding-21d-PP analysis set**” (**B21-PP**) consists of all randomized participants that are in both the “Per protocol analysis set” and the “Breastfeeding-21d-ITT analysis set”.
- The “**CRP-2-PP analysis set**” (**CRP2-PP**) consists of all randomized participants that are in both the “Per protocol analysis set” and the “CRP-2-ITT analysis set”.

Note: abbreviations, in parenthesis are used in Table 2 below.

⁶Note that data collected during a visit or phone interview occurring outside of the accepted range will be considered as missing, as already stated in Section 5.3. Accepted ranges for visit times are 1-3 days for visits related to outcomes **E6** and **E8** and 17-25 days for phone interviews related to outcome **E7**.

7 Analyses supporting the primary objectives

The main analyses for the ITT estimands will use the “All participants analysis set” and corresponds to “intention-to-treat” analyses. The main analyses for the PP estimands will use the “Per protocol analysis set” and corresponds to “per protocol analysis” analyses. Apart from the difference in analysis set being used, the PP and ITT analyses will be performed identically, as described below.

7.1 Analyses of co-primary outcome P1

We will not adjust for baseline covariates in the computation of the CIs and p-values. Specifically, we will compute the two-sided 95%-CI for the risk difference using the Miettinen-Nurminen asymptotic score interval method [19], as it has been shown to perform well and to be “safe to use” by Fagerland et al. [9], even when few events are observed. A matching p-value will be computed too. To compute the CI, we will use the `diffscoreci()` function from the `PropCIs` package of R, as suggested by Fagerland et al. [9]. To compute the p-value, we will use the `z2stat()` function of the same package; see details in Appendix A.1. This method is more appropriate than simpler (common) large sample approximations when a small to moderate number of events is expected, but it is not overly conservative [9]. The risk and risk difference estimates will be computed as the empirical (i.e., observed) proportions and their difference. Two-sided 95%-CI for the risks in each arm will be computed as exact binomial two-sided 95% CIs, using the `binom.test()` function of R.

For completeness and especially to report the timing of the readmissions, cumulative incidence plots will also be reported, as described in Section 10.1.4. Further details about each admission will also be reported, as described in Section 10.1.1.

7.1.1 Sensitivity analysis

The analysis for the PP estimand might be biased if the newborns excluded from the “Per protocol analysis set” differ from those included in it. Hence, for completeness and to assess the robustness of the results to a possible selection bias, we will perform the following sensitivity analysis.

We will report the results (p-value and upper limit of the 95% CI) assuming that zero, one, two, three, ... of the newborns excluded from the “Per protocol analysis set” in each arm have experienced the co-primary outcome **P1**. A graphical representation similar to the “Enhanced tipping-point display” presented in Liublinska et al. [18, Fig. 2] will be reported, to provide an overview of the results in these cases. It will show a heat map of the upper limit of the 95% CI (or p-value) for the different cases.

7.2 Analyses of co-primary outcome P2

The analysis of **P2** will consist of a simple unadjusted analysis to compare medians. We will estimate the median for each arm and their difference, together with two-sided 95%-CIs. Point estimates will be computed as sample medians (via the `median()` function of R) and standard errors by standard non-parametric bootstrap (using 10,000 bootstrap samples). The 95% CIs will be computed as “Est. \pm 1.96·SE”, where “Est.” denotes the point estimate and SE the corresponding standard error. Similarly, the p-value for the one-sided test will be computed using the test statistic $Z=Est./SE$, assuming that Z follows a standard normal distribution.

To complement the above analysis and for the sake of completeness, a dot plot or histogram will be reported to summarize the distribution in each arm. Quartiles of the distributions in each

arm will be reported too (e.g., boxplots will be overlaid on top of the plot). We will also consider showing on the plot the observations corresponding to the newborns who experienced the primary outcome.

8 Analyses supporting secondary objectives

The secondary outcome **S1** and corresponding estimands are similar to those of the co-primary outcome **P1**. Therefore, it will be analyzed similarly, as described in Section 7, except that no p-value will be reported (as already mentioned in Section 5.2).

9 Analyses of exploratory outcomes

The table 2 lists the analysis sets and methodology that will be used to analyze each exploratory outcome. The method will be either that used for analyzing **P2** described in Section 7.2 (i.e., non-parametric bootstrap comparison of medians, for quantitative outcomes) or that used for **S1** described in Section 8 (Miettinen-Nurminen, for binary outcomes). Note that two analysis sets are listed for each analysis, indicating that the analysis will be performed twice, using each set, to perform both PP and ITT analyses.

Outcome	Analysis set(s)	Method as for analyzing
E1	All, PP	P2
E2	All, PP	P2
E3	All, PP	S1
E4	All, PP	S1
E5	All, PP	P2
E6	B2, B2-PP	S1
E7	B21, B21-PP	S1
E8	CRP2, CRP2-PP	P2
E9	All, PP	P2
E10	All, PP	S1
E11	All, PP	S1

Table 2: Analysis of exploratory outcomes

Remarks:

- (i) Exploratory outcomes **E6** and **E7** are not binary outcomes. They are categorical outcomes, with possible values “no breastfeeding”, “partial breastfeeding” or “exclusive breastfeeding”. Hence, we will report the proportions and the between arm differences in proportions for each of these modalities. Additionally, we will also perform the analysis after dichotomizing into “no breastfeeding” vs “partial or exclusive breastfeeding”.
- (ii) The pre-specified analysis of **E6**, **E7** and **E8** are complete case analysis. For completeness and transparency, descriptive statistics will be provided, per arm, about baseline characteristics of subjects with a missing value. Any difference to subjects without missing data thought as clinically relevant will be reported.

10 Other analyses

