February 6, 2025

Signature & Date

2 List of Abbreviations

- CI: Confidence Interval
- CRP: C-reactive protein
- GBS: Group B streptococcus
- ITT: Intention-To-Treat
- PP: Per Protocol
- SAE: Serious Adverse Event
- SAP: Statistical Analysis Plan

3 Introduction

This document is the statistical analysis plan (SAP) for an open label, investigator-initiated, parallel group, 1:1 randomized, multicenter, non-inferiority clinical trial of “individualized” versus “standard” duration of antibiotic treatment for culture negative early-onset infection in term newborns. The individualized treatment duration is based on structured clinical assessment of symptoms and level of C-reactive protein (CRP). The individualized treatment duration can be as short as two days while the standard treatment duration is seven days. It is hypothesized that an individualized treatment duration will shorten the duration of antibiotic therapy in newborns with early onset infection with no or very limited increase in the risk of relapse.

The trial recruited newborns from all Departments of Neonatology in Denmark except one (17 out of 18). Stratified randomization was planned 36 to 48 hours after the treatment started using permuted blocks of size six, stratified on maximum CRP level within the last 48h above or below 90 mg/l. Patient accrual started in Spring 2022 and was anticipated to stop in January 2025, after inclusion of 488 newborns.

The changes to the protocol-planned analyses are summarized in Section 12. We do not consider them as major changes and the rationale for each of them is provided.

4 Objectives, Endpoints, and Estimands

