4.1 Primary objectives, endpoints and estimands

There are two co-primary objectives and therefore two co-primary outcomes in this trial.

The first objective is to show that an “individualized” antibiotic treatment duration is non-inferior to a “standard” treatment duration for treating culture negative early-onset infection in term newborns, with respect to the risk of readmission due to bacterial infection. By non-inferior, we mean that the risk of readmission due to bacterial infection within 28 days is not larger with the “individualized” duration than with the “standard” duration, by more than the pre-specified non-inferiority margin of 4%. The rationale for choosing this margin is provided in Section 4.1.2.

The second objective is to show that the “individualized” antibiotic treatment duration leads to less antibiotics days than the “standard” treatment duration. More specifically, the second objective is to show superiority of the “individualized” treatment duration with respect to the

median of the total duration of antibiotics use within 28 days from treatment start. Although the initial treatment duration will systematically be shorter using the “individualized” duration, relapses can happen, leading to new initiations of antibiotic treatment. Hence it remains to confirm that the median of the total duration of treatment within 28 days is shorter using the “individualized” initial duration than using the “standard” initial duration. This is precisely the second objective.

The two treatment strategies (interventions) being investigated for initial treatment are detailed below. Of note, the two strategies below are defined for newborns who have already received 36 to 48 hours of treatment, hence none can lead to a treatment discontinuation before a newborn has received at least 36 hours of antibiotic treatment.

- **Experimental (“individualized”):** discontinuation of antibiotics when both of the following two criteria are fulfilled:

1. The infant has been 24 hours without clinical symptoms of infection, after systematic clinical evaluation by a neonatologist. The clinical symptoms that are considered are those specified in Table 1 below. They are those of the “easy-to-use” scoring system originally published by Stocker et al. [24], up to minor modifications.
2. CRP is declining and $\leq 30 \text{ mg/l}$.

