4.1.1 Readmission due to bacterial infection

The first co-primary outcome (**P1**) is hospital readmission due to bacterial infection (or death, although none is expected), within 28 days after treatment started. Specifically, hospital readmission due to bacterial infection is defined as hospital readmission that fulfills all of the following:

¹By regularly we mean every 18 to 48h, typically every 24h, approximately.

²Specifically, seven days in 15 out of 17 departments, including all of the largest; five days in two departments.

- ≥ 1 clinical symptom(s), among those listed in Table 1
- CRP during readmission > 10 mg/l
- ≥ 72 hours of antibiotic treatment received following readmission

Note that there is no minimum time for the time to readmission as we define and record it. A newborn can be readmitted as early as the day of discharge or the following day.

The first co-primary clinical question of interest is: *“Is the risk of hospital readmission due to bacterial infection within 28 days after the start of treatment not more than 4% higher when using the individualized treatment duration than when using the standard duration of seven days, regardless of initiation of any additional interventions during the follow-up, when needed to ensure good clinical care?”*

To answer this question, we will use two co-primary estimands. The first corresponds to an **“intention-to-treat estimand”** and is described by the following attributes:

- Population: infants diagnosed with a probable or possible infection within 0-72 hours from birth according to a structured infection risk assessment, who have received 36 to 48h of antibiotic treatment and no positive blood culture result so far; infants are born with gestational age ≥ 35 weeks and weight ≥ 2000 g.
- Endpoint: hospital readmission due to bacterial infection (as defined above; or death) within the first 28 days after treatment initiation.
- Treatment: The investigational interventions (“individualized” vs “standard”, as defined above) regardless of any subsequent treatment decision or intervention during the follow-up needed to ensure good clinical care and regardless of adherence (“treatment policy strategy”, see [15]).

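### The P2 bootstrap ignores the CRP strata used in randomization, so its interval can be somewhat too wide if antibiotic duration depends on CRP stratum

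*SAP*

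**What the plan says.** - **Allocation** (SAP Section 3): the trial is a "parallel group, 1:1 randomized, multicenter, non-inferiority clinical trial", randomized "using permuted blocks of size six, stratified on maximum CRP level within the last 48h above or below 90 mg/l".
- **P2 analysis** (Section 7.2): sample medians and their difference, with "standard errors by standard non-parametric bootstrap (using 10,000 bootstrap samples"), then estimate ± 1.96 SE. Resampling within each arm is the natural reading, although it is not spelled out. Strata are not mentioned. Section 9, Table 2 reuses the method for E1, E2, E5, E8 and E9.
- **Individualized strategy** (Section 4.1): besides 24 hours without symptoms, stopping requires that "CRP is declining and" no higher than 30 mg/l.
- **Standard strategy** (Section 4.1, footnote in 4.1.1): nearly fixed, at "seven days in 15 out of 17 departments" and five days in the other two.
- **Covariates** (Section 5.4): the SAP recognizes that stratified allocation would normally call for adjustment. It declines this for P2 because power is very large, because "we are not aware of well-known, model-robust and recommended methods using covariate adjustment to compare medians", and because an unadjusted ITT comparison is generally conservative for superiority.

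**The concern.** Stratified blocks hold the high-CRP share almost equal in the two arms. A bootstrap that ignores strata lets the share move independently in each arm, so it puts back variation that the design removed. This matters only if P2 differs between strata. In the individualized arm it probably does, because an infant who starts above 90 mg/l has further to fall to the CRP threshold for stopping.

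The P2 median difference with its 95% CI is the trial's estimate of antibiotic time saved, so the calibration of that interval is at stake. The reasons in Section 5.4 concern the power and direction of the test, and covariate-adjusted estimators. They do not address a change to the variance alone, which leaves the medians, the point estimate and the estimand as they are. The sparse-event argument in the same section is made for P1.

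**Working it through.** **Inputs from the SAP.** Allocation is 1:1 in blocks of six within two strata. The total follows from Section 11.1: 207/(1 − 0.15) = 243.5, so 244 per arm and N = 488. The SAP states no SE, interval width or power for P2, so there is no P2 figure to reproduce.

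**Assumed inputs, because the SAP gives none.** Standard arm about 168 h, SD 8 h. Individualized arm log-normal with log SD 0.25, median 72 h at low CRP and 72-144 h at high CRP. Share p above 90 mg/l of 15-40%.

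**Large-sample formula, individualized arm only.** Let m be the arm's overall median, f the density there, and g the difference between strata in the probability of lying below m. Let v = p(1 − p)g².

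- Bootstrap ignoring strata: variance = 0.5/(N f²).
- Stratified 1:1 allocation: variance = (0.5 − v)/(N f²). Half of the between-stratum part 2v is removed. The rest stays because the overall stratum share is still random.
- Ratio of SEs = √[0.5/(0.5 − v)].

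Worked cases:

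- 25% high CRP, 120 h: m = 79.3 h. P(below m) = Φ(ln(79.3/72)/0.25) = 0.650 at low CRP and Φ(ln(79.3/120)/0.25) = 0.049 at high CRP. So g = 0.602, v = 0.25 × 0.75 × 0.602² = 0.068, and the ratio is √(0.5/0.432) = 1.08.
- 40% high CRP, 144 h: m = 90.0 h, probabilities 0.813 and 0.030. So g = 0.783, v = 0.24 × 0.783² = 0.147, and the ratio is √(0.5/0.353) = 1.19.
- No CRP effect: g = 0, ratio 1.00.

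**Simulation with the actual block design** (4,000 reference trials and 500 bootstrapped trials per scenario). The last three columns are SE divided by the true SD of the median difference:

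| High-CRP share, median | Formula | Planned bootstrap | Pooled stratum sizes, split 1:1 | Fixed stratum sizes |
|---|---|---|---|---|
| 25%, 72 h (no effect) | 1.00 | 1.00 | 1.00 | 1.00 |
| 25%, 96 h | 1.03 | 1.03 | 1.00 | 0.97 |
| 15%, 120 h | 1.04 | 1.05 | 1.01 | 0.97 |
| 25%, 120 h | 1.08 | 1.12 | 1.05 | 0.97 |
| 40%, 120 h | 1.13 | 1.17 | 1.05 | 0.90 |
| 40%, 144 h | 1.19 | 1.22 | 1.02 | 0.77 |

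The simulated ratios are good to a few hundredths. They also include some finite-sample upward bias of the bootstrap SE of a median: under a different, more skewed duration model the planned ratio was 1.04 with no CRP effect at all. The formula column isolates the part due to the strata.

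**In hours, at 40% and 144 h.** Planned SE 4.0 h, design-matched SE 3.3 h, true SD 3.2 h. The full CI width is 2 × 1.96 × 4.0 = 15.7 h against 2 × 1.96 × 3.3 = 12.9 h, on a difference of about 168 − 90 = 78 h. Z is about 78/4.0 = 19.5 in absolute value.

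**Coverage of the nominal 95% interval** (1,600 trials per scenario). Planned 0.951-0.974; pooled-size scheme 0.941-0.954.

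**The case against.** **This is a disclosed choice.** Section 5.4 names the stratification and accepts an unadjusted, conservative analysis. That stands: it is not an oversight. A reader might infer that the 5.4 sentence on methods for medians is wrong. It is not. It speaks only of well-known, recommended methods that use covariate adjustment, and a design-matched SE is not one of those.

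**The replacement may undercover.** In a simulation of 1,000 trials per scenario (Monte Carlo SE about 0.007), the pooled-size scheme covered 0.934-0.940 at shares of 15-25%, where the planned interval covered 0.945-0.953. At 40% it covered 0.948-0.953 against 0.973-0.975. The larger run gave 0.941-0.954. Overall the scheme sits at or slightly below nominal, so its coverage should be called approximate. Marked narrowness belongs to a different scheme, resampling with fixed stratum sizes (ratio down to 0.77).

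**The largest excess needs extreme inputs.** A 144 h median with log SD 0.25 puts 1 − Φ(ln(168/144)/0.25) = 27% of high-CRP individualized infants beyond seven days, whereas Section 12 describes the strategy as lasting two to seven days. Capping that tail would barely move the overall median, but the scenario is an upper end and not an expectation.

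**Balance is guaranteed only by randomization.** Section 11.1 allows up to 15% of infants to fall outside the PP set, and E8 is a complete-case analysis. A 1:1 split within stratum is not a design property there. This stands, and those sets need a separate rule.

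**Conclusion.** The point holds as a conditional and minor one. The Section 7.2 bootstrap does not match the stratified design, and the P2 interval can be too wide if duration in the individualized arm depends on CRP stratum. Under the assumed inputs the SE excess is zero with no CRP effect, roughly 3-12% with 15-25% high-CRP infants, and about 13-22% only with a strong effect and 40% high-CRP infants.

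The documents do not support three stronger readings that a reader might draw:

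- **That the interval will be too wide whatever the data.** The excess vanishes if CRP stratum is unrelated to duration, and the SAP gives neither the size of that relation nor the stratum share.
- **That the P2 conclusion is at risk.** The error is conservative, so type I error is not inflated. With Z of about 13 to 46 in absolute value across another set of assumed scenarios, superiority would be concluded either way.
- **That E1, E2, E5, E8 and E9 are all affected.** They share the method, but the excess was not shown for them and arises only where the outcome depends on CRP stratum.

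**What to change.** **Section 7.2, ITT set.** Keep the sample medians and their difference. In each of the 10,000 bootstrap samples, draw the two CRP-stratum sizes from the pooled sample, split each stratum 1:1 between arms, and resample infants within arm by stratum. Do not hold the stratum sizes fixed, because that can make the SE too small.

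**PP and complete-case sets.** State one rule in advance: split each stratum by the observed arm shares within it, or keep the standard bootstrap.

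**Table 2 outcomes.** Apply the scheme to E1, E2, E5, E8 and E9 for consistency, noting that a gain is expected only where the outcome depends on CRP.

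**Section 5.4.** Keep the sentence on covariate-adjusted methods for medians, and add that a design-matched standard error needs no covariate adjustment.

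**Cost.** A few lines of R and a short SAP edit. The stratum was needed for randomization, so no new data are required, and the estimand does not change. The price is a coverage that is approximate, about 94-95% in simulation, in place of one that is at or above nominal.
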